5.4 Demographic Characteristics

Baseline conditions and demographics will be analysed with descriptive statistics. Age at start of afatinib (Gi(l)otrif[®]) will be calculated as the number of complete years between a subject's birth date and the start date of initial dose of afatinib (Gi(l)otrif[®]). BMI will be calculated as follows:

$$BMI = \frac{\text{weight (kg)}}{\text{height (m)}^2}$$

- A summary of demographic variables (e.g. age at start of afatinib (Gi(l)otrif[®]), sex, ethnicity, race, country, region, height, weight and BMI at start of afatinib) will be provided. This summary will be repeated for Ethnicity and Race subgroups. T14.1.2.1
T14.1.2.2
T14.1.2.3

A by-patient listing with the demographic characteristics will be provided. L16.2.4

5.5 Disease Characteristics

The collection of data will be divided between first line treatment – afatinib (Gi(l)otrif[®]) – and second line treatment – osimertinib.

5.5.1 First Line Treatment – Afatinib

The frequency of the different types of mutations at the initial diagnosis – Del19 and L858R, others or both – and the stage of disease at start of afatinib (Gi(l)otrif[®]) will be summarized. T14.2.1.1

This analysis will be repeated for the Race subgroup. T14.2.1.2

The number and percentage of patients with metastases at start of afatinib (Gi(l)otrif[®]) will be provided by site of metastases. T14.2.1.3

The brain metastases summary will be repeated for the Race subgroup. T14.2.1.4

The ECOG PS at start of afatinib (Gi(l)otrif[®]) will be summarized in terms of number and percentage of patients with ECOG PS equal to 0, 1, 2, 3, 4, 5 or missing. T14.2.1.5

This analysis will be repeated for the Race subgroup. T14.2.1.6

The starting afatinib (Gi(l)otrif[®]) dose will be summarized through descriptive statistics. T14.2.1.7
This analysis will be repeated for the Race subgroup. T14.2.1.8

The frequency and number of dose modifications, reductions and increases of afatinib (Gi(l)otrif[®]) and the reason for change will also be summarized. T14.2.1.9

Statistical Analysis Plan Template For Observational Studies

Boehringer Ingelheim
Protocol c14668275-02

Statistical Analysis Plan

When a patient receives no drug for at least 14 days this will be considered a treatment interruption and will be derived using the end date of one dose and the start date of the next dose.

The frequency of treatment interruptions and the frequency and reason for treatment discontinuation will be provided. T14.2.1.10

By-patient listings with the following information will be provided:

- Type of mutations at the initial diagnosis, stage of disease, site of metastases and ECOG PS at start of afatinib. L16.2.6.1

- Start and end date of initial dose and the respective dose, start and end date of all modified doses and the respective doses and the reasons for dose modification(s); reason for treatment discontinuation. L16.2.6.2

5.5.2 Second Line Treatment – Osimertinib

The frequency of the different types of mutations at start and stop of osimertinib – Del19, L858R, both, T790M and other mutations – will be summarized. T14.2.2.1

This analysis will be repeated for the Race subgroup. T14.2.2.2

The type of mutations at stop of osimertinib will be analysed according to section 5.6.2.

The number and percentage of patients with metastases at start of osimertinib will be provided by site of metastases. T14.2.2.3

This analysis will be repeated for the Race subgroup. T14.2.2.4

The ECOG PS at start of osimertinib will be summarized in terms of number and percentage of patients with ECOG PS equal to 0, 1, 2, 3, 4, 5 or missing. T14.2.2.5

This analysis will be repeated for the Race subgroup. T14.2.2.6

The number and percentage of patients that, for treatment with osimertinib, used the regular clinical practice program or did it through EAP/CUP will be summarized. T14.2.2.7

The starting osimertinib dose will be summarized through descriptive statistics. T14.2.2.8

This analysis will be repeated for the Race subgroup. T14.2.2.9

The frequency and number of dose reductions and increases, and both of osimertinib and the reason for change will also be summarized. T14.2.2.10

The frequency of treatment interruptions and the frequency and reason for treatment discontinuation will be provided. T14.2.2.11

Statistical Analysis Plan Template For Observational Studies

Boehringer Ingelheim
Protocol c14668275-02

Statistical Analysis Plan

A summary analysis of patients for which metastases were developed or disappeared from start of Afatinib to start of Osimertinib will be provided. T14.2.2.12

A shift table of ECOG PS from start of Afatinib to start of Osimertinib will be displayed. T14.2.2.13

By-patient listings with the following information will be provided:

- Type of mutations, site of metastases and ECOG PS at start of osimertinib and the program used for treatment with osimertinib. L16.2.6.3

- Start and end date of initial dose and the respective dose, start and end date of all modified doses and the respective doses and the reasons for dose modification(s); reason for treatment discontinuation. L16.2.6.4

- Type of mutations at stop of osimertinib, before classification and categorization. L16.2.6.5

5.6 Statistical methods

5.6.1 Analysis of the Primary Outcome

The primary outcome is time on treatment, which is defined as time in months from the start date of afatinib (Gi(l)otrif[®]) treatment – ‘start date of initial dose’ for First Line Treatment – to the end date of osimertinib treatment – maximum between ‘end date of initial dose’ and the last ‘end date of dose modification’ for Second Line Treatment – or death date due to any cause – ‘date of death’.

$$\text{Time on treatment (months)} = \text{time on treatment (days)} / 30.4375$$

Time on treatment will be analysed using Kaplan-Meier method, and the median along with two-sided 90% confidence interval will be displayed using the Greenwood’s formula for estimation of standard errors.

The primary outcome will be analysed in SAS using the LIFETEST procedure as follows:

```
proc lifetest data=mydata alphaqt=0.1  
  plots=survival(atrisk failure);  
  time t*event(0);  
run;
```

where **alphaqt** specifies the 90% confidence interval; the **t** variable is the time in months from the start date of afatinib (Gi(l)otrif[®]) treatment to the end date of osimertinib treatment or death; and the **event** variable specifies the subjects for which the whole information is present (=1) or were censored (=0). T14.2.3.1

The time on treatment (afatinib, osimertinib and total) will be summarized through descriptive statistics and survival plots will be provided. F14.2.3.5

Statistical Analysis Plan Template For Observational Studies

Boehringer Ingelheim
Protocol c14668275-02

Statistical Analysis Plan

Both tables and plots will be repeated for the following subgroups: Ethnicity, Race, EGFR mutation, Gender, Brain metastases at start of Afatinib, Brain metastases at any time, Age group 1, Age group 2, ECOG and Data Source. T14.2.3.2
F14.2.3.6
T14.2.3.8
F14.2.3.10

For the subgroup analyses, the log-rank test results will be provided. These results may be obtained introducing the strata statement in the LIFETEST procedure as follows: T14.2.3.12
F14.2.3.14

```
proc lifetest data=mydata alphaqt=0.1  
  plots=survival(atrisk failure);  
  time t*event(0);  
  strata subgroup;  
run;
```

For the total time on treatment, the information on the number and percentage of censored patients will also be summarized. T14.2.3.3

This table will be repeated for the following subgroups: Ethnicity, Race, EGFR mutation, Gender, Brain metastases at start of Afatinib, Brain metastases at any time, Age group 1, Age group 2, ECOG and Data Source. T14.2.3.4

Time between end of afatinib and start of osimertinib will be summarized through descriptive statistics. T14.2.3.15

Time between end of osimertinib and death will be analyzed in a similar way as the primary outcome. T14.2.3.16
F14.2.3.17

Swimmer plots displaying time on afatinib treatment, time between end of afatinib and start of osimertinib and time in osimertinib treatment for each patient will be provided. F14.2.3.18

By-patient listings will be provided including at least the time on treatment (afatinib, osimertinib and total), time between end of afatinib and start of osimertinib, time between end of osimertinib and death and information whether the patient was censored or not. L16.2.6.6
L16.2.6.7
L16.2.6.8

5.6.2 Analysis of the Secondary Outcome

Different types of resistance mutations identified at the time of discontinuation of osimertinib treatment will be systematically reviewed and categorized by the trial Medical Monitor. The proportion of patients with different types of mutations after categorization will be summarized descriptively through number and percentage of patients. T14.2.4.1

A pie chart with the different types of mutations after categorization will be provided. F14.2.4.3

Both table and plot will be repeated for the following subgroup: Ethnicity, Race, EGFR mutation, Gender, Brain metastases at start of Afatinib, Brain metastases at any time, Age group 1, Age group 2, ECOG and Data Source. T14.2.4.2
F14.2.4.4

Statistical Analysis Plan Template For Observational Studies

Boehringer Ingelheim
Protocol c14668275-02

Statistical Analysis Plan

A listing will be provided with the information on the resistance mutations at the time of discontinuation of osimertinib (before and after categorization).

L16.2.6.9

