3.2 Full Analysis Set

The full analysis set (FAS) includes all patients who were enrolled into the study, met all inclusion criteria and did not meet any exclusion criteria and provided a written and signed informed consent (if a written informed consent is required for this NIS by local regulation and legal requirement). The FAS will be used for all the analyses performed during this study.

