3.5 Study Outcomes

3.5.1 Data Collected

The following data will be collected from medical records and will be recorded in the electronic case report form (eCRF) by investigators (or designees) during the study period:

- Informed consent
- Demographics: age at start of afatinib (Gi(l)otrif[®]) treatment, gender, ethnicity and race
- Type of mutations at initial diagnosis
- Stage of disease (IIIb or IV) at start of afatinib (Gi(l)otrif[®]) treatment
- Sites of metastases at start of afatinib (Gi(l)otrif[®]) treatment
- Eastern Cooperative Oncology Group (ECOG) performance score (PS) (if available) at start of afatinib (Gi(l)otrif[®]) treatment
- Body weight and height at start of afatinib (Gi(l)otrif[®]) treatment
- Date of start and end of afatinib (Gi(l)otrif[®]) treatment
- Starting dose of afatinib (Gi(l)otrif[®])
- Afatinib (Gi(l)otrif[®]) dose modification(s) and respective date(s)
- Reason for discontinuation of afatinib (Gi(l)otrif[®]) treatment (e.g. progressive disease (PD), adverse event (AE))
- Type of mutations at start of osimertinib treatment
- Sites of metastases at start of osimertinib treatment
- ECOG PS (if available) at start of osimertinib treatment
- Type of mutations at stop of osimertinib if available (EGFR mutations: T790M, C797S [if positive: in cis or in trans], Del19, L858R, other EGFR sensitizing mutation (to be specified), non-EGFR: to be specified) (R16-1552, P15-11024)
- If osimertinib was provided within an EAP/CUP or prescribed as clinical practice
- Date of start and end of osimertinib treatment
- Starting dose of osimertinib
- Osimertinib dose modification(s) and date(s)
- Reason for discontinuation of osimertinib treatment (e.g. PD, AE)
- Subject status at data entry completion
- Date of death (if available) / Date patient was last known to be alive (if available)
- Date of consent withdrawal (if applicable)
- All ADRs (independently from the outcome) and AEs with fatal outcome with respective start and end dates, severity, outcome, seriousness and relationship to afatinib (Gi(l)otrif[®])

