3.5.3 Secondary Outcome

Type and proportion of acquired resistance mutations after osimertinib.

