4 DATA SOURCE

Data will be collected from patients' medical records and recorded in (e)CRFs.

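### Resistance percentages after osimertinib have no denominator of patients tested for each alteration, so any alteration that not every routine test covered is understated

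*SAP*

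**What the plan says.** The only secondary outcome, in SAP section 3.5.3, is "Type and proportion of acquired resistance mutations after osimertinib". The data are not generated by the study. Section 4 says: "Data will be collected from patients' medical records and recorded in (e)CRFs". Section 3.5.1 lists the relevant item as "Type of mutations at stop of osimertinib if available (EGFR mutations: T790M, C797S [if positive: in cis or in trans], Del19, L858R", followed by other sensitizing EGFR mutations and "non-EGFR: to be specified". The list contains no specimen type, assay, set of genes covered or not-tested status.

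Section 5.6.2 starts from positive findings: "Different types of resistance mutations identified at the time of discontinuation of osimertinib treatment will be systematically reviewed and categorized". It then gives the statistic: "The proportion of patients with different types of mutations after categorization will be summarized descriptively through number and percentage of patients". It names no denominator. Section 3.2 sets the population: "The FAS will be used for all the analyses performed during this study".

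Two general rules could supply the denominator, and they disagree. Section 5.2 bases percentages on non-missing data. Section 5.8 bases percentages for categorical variables on all patients, with or without data.

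The output is repeated by subgroup: "Both table and plot will be repeated for the following subgroup: Ethnicity, Race, EGFR mutation, Gender", continuing to ten factors in all. Section 3.4 defines the Ethnicity factor by country (three Asian countries against eight others) and Data Source as Cardinal Health against the other clinical sites.

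**The concern.** A proportion of patients with an alteration is interpretable only over patients in whom it could have been found. Section 3 plans for around 65 centres in 11 countries, each contributing whatever test was done in practice. A test limited to certain EGFR variants returns a real result, so the patient is not obviously missing, yet it says nothing about an alteration outside its scope. If that patient stays in the denominator, the alteration looks rarer than it is, and the less often it is tested the rarer it looks.

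This differs from the question of patients with no stop test at all. Restricting the table to tested patients would settle that question and leave this one open.

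The percentage is the whole of the secondary result, so its denominator decides what the study reports on resistance. Two of the subgroup factors, region and Data Source, sort patients by where they were treated or where their data came from. Any difference in local testing would fall along those lines.

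**Working it through.** **The plan's own figures.** The SAP gives no expected proportion, number tested or test coverage for this outcome. Its only computed design figure is the sample size in section 5.9: 171 / (1 − 0.10) = 190, which reproduces. It belongs to the primary outcome and serves here only as the FAS size in the illustration.

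**Which patients are in the denominator?** Take a patient with a stop result from a test that did not cover alteration X.

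- Section 5.8 rule: patients with and without data are counted, so this patient is in. So are patients with no stop test, including those still on osimertinib.
- Section 5.2 rule, stop mutation held as one variable, or blanks read as negative: the patient has a result, so is non-missing and is in.
- Section 5.2 rule, each alteration its own field, left blank when untested: the patient is missing for X and is out. Only this arrangement gives the right denominator, and the SAP does not say that it applies.

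**Inputs.** N = 190 (section 5.9). Assumed, because the SAP gives none of them:

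- p, the true proportion among tested patients: 10% to 30%
- c, the share of stop tests able to detect X: 40% to 100%
- t, the share of the FAS with a stop test: 20% to 60%

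Coverage is taken as unrelated to mutation status, and a test that covers X is taken to detect it.

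**Formulas.** Number detected = N × t × c × p. Dividing by each candidate denominator gives:

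- all FAS patients (N): p × c × t
- tested patients (N × t): p × c
- patients tested for X (N × t × c): p

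**Worked case, p = 20%, t = 40%.** Tested = 190 × 0.40 = 76.

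| | c = 40% | c = 80% |
|---|---|---|
| Tested for X | 76 × 0.40 = 30.4 | 76 × 0.80 = 60.8 |
| Detected | 30.4 × 0.20 = 6.08 | 60.8 × 0.20 = 12.16 |
| Over FAS (5.8) | 6.08 / 190 = 3.2% | 12.16 / 190 = 6.4% |
| Over tested (5.2, single variable) | 6.08 / 76 = 8% | 12.16 / 76 = 16% |
| Over tested for X | 6.08 / 30.4 = 20% | 12.16 / 60.8 = 20% |

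**Range over tested patients (p × c).**

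| True p | c = 40% | c = 80% | c = 100% |
|---|---|---|---|
| 10% | 4% | 8% | 10% |
| 20% | 8% | 16% | 20% |
| 30% | 12% | 24% | 30% |

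Over the whole FAS each entry is multiplied again by t. For p = 20% and c = 40%, this gives 0.08 × 0.20 = 1.6% at t = 20% and 0.08 × 0.60 = 4.8% at t = 60%.

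**Subgroups.** With the same true 20% in two subgroups and coverage of 80% in one and 40% in the other, the tested-patient table shows 16% against 8%, a two-fold contrast from coverage alone. With equal coverage the spurious difference is zero.

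**The case against.** The strongest counter-argument is that the deciding documents are not at hand. Section 3.5.1 summarises what is collected; it is not the CRF. Its wording on C797S, which asks for cis or trans only when the result is positive, suggests a result field, and that field may offer a not-tested option. If each mutation has its own field and untested ones are blank, section 5.2 already gives the denominator asked for here. This stands. It means that wrongly counting uncovered patients as negative is a consequence of some readings of the plan, not an established fact. It does not rescue section 5.8, which keeps patients with missing data in, and section 5.6.2 does not choose between the two rules.

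A reader might infer that every reported proportion and subgroup contrast would reflect testing as much as resistance. The documents do not support that. They give no coverage or prevalence, the effect differs by alteration, and it vanishes where all tests cover the alteration. Nor do they say that testing differs between regions or data sources, so the two-fold contrast is a possibility on assumed inputs.

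It is also fair to say that the outcome is descriptive, that no test is planned for these subgroup tables (the log-rank test in section 5.6.1 concerns time on treatment), and that by-patient listings show the mutations before and after categorization. That lowers the stakes. It does not correct the percentage, which is what will be quoted. Finally, incomplete testing is an ordinary limit of real-world data, but dividing by patients whose test could not have been positive is an analysis choice that the SAP can change.

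**Conclusion.** The point holds in limited form. Section 5.6.2 reports patient percentages from routine tests without tying each denominator to the patients tested for that alteration. Under section 5.8, and under section 5.2 unless alterations are separate fields left blank when untested, the proportion is understated for any alteration that not all tests covered.

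Among tested patients the reported value is the true one times coverage; under section 5.8 it is multiplied again by the share tested. These sizes rest on assumed coverage, prevalence and testing rates, on coverage being unrelated to mutation status, and on covered alterations being detected. They show direction and possible scale, and do not predict this study's results. Region and Data Source tables could differ through testing alone; the SAP gives no evidence that they will.

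**What to change.** In section 5.6.2, state that the rules in sections 5.2 and 5.8 do not apply to T14.2.4.1 and T14.2.4.2. For each alteration, report the number of patients with it detected over the number tested for it, and show not tested and unknown as separate counts. Use the CRF result fields if they already carry this status; the change is then SAP and table-shell wording only. If they do not, add a tested/not-tested item taken from the existing report where feasible.

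If test scope cannot be established, report only counts of detected alterations, labelled as minimum counts, without percentages. Label all subgroup repeats as dependent on testing, not just those by region and Data Source, because coverage may vary across other factors too. The pie charts should carry the same label, since a pie cannot show a different denominator for each slice.

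The costs are smaller and varying denominators, and some re-abstraction across around 65 centres if a field is added. In the worked case, the standard error at 20% is √(0.2 × 0.8 / 30.4) = 7.3 percentage points at 40% coverage and √(0.2 × 0.8 / 60.8) = 5.1 points at 80%. That is the precision the data actually hold for such an alteration. The change does not remove selection in who was tested, and if wider tests were ordered in patients more likely to carry an alteration, the new proportion would still be affected. The report should say so.

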5.7 Safety Data

There was no initial intention to analyze the safety data collected retrospectively in the study as part of the study analysis. The safety data from this study was reviewed and analysed as part of routine global pharmacovigilance processes but at a later point it was also requested by regulatory authorities that AE data is statistically analyzed.

An overview AE table containing at least number of patients and events with AEs, serious AEs, severe AEs will be produced. AE summary tables by severity, SOC and PT, SOC and PT or by PT only will be provided for all AEs, study treatment-related AEs, serious AEs, study treatment-related serious AEs, serious AEs with fatal outcome and study treatment-related serious AEs with fatal outcome.

T14.3.1
T14.3.2
T14.3.3
T14.3.4
T14.3.5
T14.3.6
T14.3.7
T14.3.8
L16.3.1
L16.3.2

By-patient listings will be provided for all AEs and serious AEs, including AEs with fatal outcome.

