5.2 General Presentation Considerations

No study visits are expected on this study. The 'Date of Visit' page in eCRF will include only the information of the first day of data entry.

Continuous data will be summarized in terms of the mean, standard deviation (SD), median, minimum, maximum and number of observations, unless otherwise stated. Continuous data that are expected to be skewed will be presented in terms of the maximum, upper quartile, median, lower quartile, minimum and number of observations. The minimum and maximum will be reported to the same number of decimal places as the raw

Statistical Analysis Plan Template For Observational Studies

Boehringer Ingelheim
Protocol c14668275-02

Statistical Analysis Plan

data recorded in the database. The mean, median, lower quartile and upper quartile will be reported to one more decimal place than the raw data recorded in the database. The SD will be reported to two more decimal places than the raw data recorded in the database. In general, the maximum number of decimal places reported shall be four for any summary statistic. The number of decimal places to be displayed in each output will be specified in the Tables, Listings and Figures (TLF) shells document.

Categorical data will be summarized in terms of the number of patients providing data at the relevant time point (n), frequency counts and percentages. The number of patients with missing information for a specific variable will be displayed if applicable. Any planned collapsing of categories will be detailed in the SAP text and the data displays. Percentages will be presented to one decimal place. Percentages will not be presented for zero counts. Percentages will be calculated using non-missing data as the denominator.

Confidence intervals will be presented to one more decimal place than the raw data.

All report outputs will be produced using SAS® version 9.3 or a later version in a secure and validated environment. All report outputs will be provided to BI in a single Microsoft Word document.

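### SAP section 5.7 plans unrestricted AE and serious AE outputs, but section 3.5.1 lists only ADRs and fatal AEs as recorded, with causality to afatinib alone

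*SAP*

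**What the plan says.** Section 3.5.1 (Data Collected) lists the items to be taken from medical records and entered in the eCRF. The only item that records safety events as events is "All ADRs (independently from the outcome) and AEs with fatal outcome with respective start and end dates, severity, outcome, seriousness and relationship to afatinib". Elsewhere in the list, AE appears only as an example reason for stopping afatinib or osimertinib, as in "Reason for discontinuation of osimertinib treatment (e.g. PD, AE".

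Section 5.7 (Safety Data) explains that the AE analysis came later: "There was no initial intention to analyze the safety data collected retrospectively in the study as part of the study analysis". Regulators subsequently asked for a statistical analysis. The section then plans three kinds of output:

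- an overview: "An overview AE table containing at least number of patients and events with AEs, serious AEs, severe AEs will be produced";
- summary tables that "will be provided for all AEs, study treatment-related AEs, serious AEs, study treatment-related serious AEs", followed by serious AEs with fatal outcome and the treatment-related version of these;
- listings: "By-patient listings will be provided for all AEs and serious AEs, including AEs with fatal outcome".

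No sentence in section 5.7 restricts these outputs to ADRs and fatal AEs, and none defines study treatment-related.

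**The concern.** The SAP treats ADR and AE as different terms. The abbreviation list defines them separately, and the section 3.5.1 bullet uses the first for events of any outcome and the second only for fatal ones. Section 5.7 names the wider class, and shows all AEs and serious AEs apart from their treatment-related versions. A reader of the finished tables would therefore expect the overall rows to include non-fatal events that nobody attributed to a drug. The collection list gives no place for such events.

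These tables exist because regulators asked for them. If the section 3.5.1 list is complete, a table titled as all AEs or serious AEs would be read as overall occurrence when it shows a selected part of it. Likewise, a table titled study treatment-related, in a study of two drugs given in sequence, would be read as covering both drugs when the listed causality field covers one.

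**Working it through.** There is no stated figure to reproduce. The check compares what is recorded with what is tabulated.

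1. **Is the collection list open or closed?** Section 3.5.1 introduces its items without wording such as at least or including. As written it is closed. Section 3.1.3 points the same way: it justifies the 10-month threshold partly by the wish for mature data on ADRs.

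2. **What is recorded?** Let A be the ADRs and F the fatal AEs. Recorded events = A ∪ F. Not recorded = AEs that are neither in A nor in F, that is, non-fatal events not judged ADRs, including any that were serious or severe. Seriousness and severity are attributes of recorded events; they are not separate grounds for recording one.

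3. **What follows for each output, if the list is complete?**

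| Section 5.7 output | Effect of the collection rule |
|---|---|
| Overview: AEs, serious AEs, severe AEs (patients and events) | Non-fatal events not judged ADRs are absent |
| Summary tables: all AEs, serious AEs | Same |
| Listings: all AEs, serious AEs | Same |
| Summary tables: treatment-related AEs, treatment-related serious AEs | Rule does not exclude afatinib-related events; label is wider than the causality field |
| Summary table: serious AEs with fatal outcome | Rule does not exclude fatal events |
| Summary table: treatment-related serious AEs with fatal outcome | Rule does not exclude fatal events; label is wider than the causality field |

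4. **Direction and size.** A patient whose only events are unrecorded drops out of the patient count. A patient with another recorded event stays in it but loses events. Recorded counts therefore cannot exceed the true ones. Section 3.2 uses the FAS for all analyses, so the denominator does not shrink to match. If the FAS had the 190 patients planned, each patient missed would lower a row by 100/190 = 0.53 percentage points. The SAP gives no basis for how many are missed, and event counts are not limited by the number of patients.

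5. **The causality label.** Three of the summary categories carry it: related AEs, related serious AEs and related serious AEs with fatal outcome. With relationship to afatinib as the only listed field, they can be produced only as afatinib-related. The SAP does not say whether osimertinib ADRs are recorded. Any that were, and were not judged related to afatinib, would appear in the overall outputs but not in these three.

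**The case against.** The strongest reply is that a SAP can tabulate only what was recorded. Section 5.7 opens by referring to the safety data collected in the study, so all AEs may simply mean all recorded events. On that reading no analysis is wrong and only a title or footnote is missing. This largely stands, and it is why the remedy is a matter of labels. It does not remove the point, because the SAP never states the restriction, and a reader of the tables should not have to infer it.

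A second reply is that unseen documents may resolve the matter. CRF Version 3.0, named in section 1, could record more than section 3.5.1 lists. That also stands, and the conclusion is conditional on it. Even then one section needs an edit, because the section 3.5.1 bullet would be too narrow. The TLF shells are a weaker answer: section 5.2 says only that the number of decimal places "will be specified in the Tables, Listings and Figures (TLF) shells document".

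A reader might also infer that the discontinuation tables will contradict the AE outputs. Section 5.5.1 says "The frequency of treatment interruptions and the frequency and reason for treatment discontinuation will be provided", and section 5.5.2 says the same for osimertinib. A patient who stopped for a non-fatal AE not judged an ADR could count there and have no recorded event. This is possible but not shown: AE is only an example reason in section 3.5.1, and nothing in the SAP indicates that such patients exist.

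**Conclusion.** The two sections do not agree, and nothing else in the SAP reconciles them. If the section 3.5.1 list is complete, the all, serious and severe AE counts of patients and events understate overall occurrence by an amount that cannot be derived from the SAP, and study treatment-related can mean only afatinib-related. If the CRF captured all AEs, section 3.5.1 is the section to correct.

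Three stronger readings go beyond the documents:

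- That the fatal-outcome tables are complete. The collection rule does not exclude fatal events, but the data come from existing medical records and even the date of death is recorded only if available.
- That the fatal share of AEs will be overstated. Section 5.7 names no such ratio as an output.
- That there would be no under-recording at all if the CRF took every AE. Events never written in the chart would still be absent.

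Severity is minor. Safety is not among the objectives in section 2, and no primary or secondary estimate changes.

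**What to change.** Reconcile sections 3.5.1 and 5.7 against CRF Version 3.0.

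If section 3.5.1 is right:

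- Describe the section 5.7 outputs as recorded ADRs and fatal AEs, with their serious and severe subsets.
- Add a footnote that non-fatal events not judged ADRs were not collected, so overall AE and serious AE incidence is not estimable.
- Rename the three related categories afatinib-related.

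If the CRF captured all AEs, correct the safety bullet in section 3.5.1 and keep the AE wording of section 5.7.

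Optionally, compare patients whose discontinuation reason is AE (L16.2.6.2 and L16.2.6.4) with the AE listing in section 5.7, to see whether any has no recorded event.

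The cost is some wording and one footnote, or one corrected bullet. No new data are needed and no output is dropped. The only drawback is that the output titles become less general.
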